**b Introduction:**

Hypertension (HT) is an important risk factor for stroke, coronary heart disease (CHD), heart failure and renal diseases, and the leading risk factor of global disease burden. A multitude of interventions have proven efficacy in lowering blood pressure and reducing long term HT complications, including pharmacologic treatment, DASH diet (Dietary Approaches to Stop Hypertension), exercise, weight reduction, smoking cessation, alcohol moderation and self-monitoring of blood pressure. A few studies had examined the effects of coordinated multidisciplinary management programmes for HT patients to maximize the effectiveness of these interventions, but the long term benefit or cost-effectiveness of such programmes are uncertain.

In Hong Kong, over 200,000 patients with HT are being managed in public primary care clinics (i.e. General Out-patient Clinics (GOPCs) and Family Medicine Clinics (FMC)) under the Hospital Authority (HA); but more than 45% HT patients have still not achieved target blood pressure control (HA Internal communication). In order to improve the quality of care for patients with uncontrolled HT at GOPCs, the evidence-based , structured protocol-driven multidisciplinary Risk Assessment and Management Programme – Hypertension (RAMP-HT) was launched since October 2011 by the HA with the support from the Food and Health Bureau. Standardized cardiovascular risk factor assessment, hypertensive complication screening and assessment on patient adherence to treatment are carried out on enrolled patients (Appendix A). Patients are stratified into low,

medium or high risk groups according to the 10-year cardiovascular disease (CVD) risk calculated from their relevant risk factors by the Joint British Society 2005 Equation. A multidisciplinary team comprised of doctors, nurses, dieticians, physiotherapists and/or occupational therapists would then deliver individualized management targeted to the patient's risk factors according to standardized risk-stratified guidelines (Appendix B).

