#### Exclusion criteria

1. Patients who had a diagnosis of any HT complications defined by relevant ICPC-2 and/or ICD-9-CM diagnosis codes (defined in the "Methods" section) on or before baseline\*
2. Patients diagnosed to have Diabetes Mellitus (DM) on or before 31 March 2017, defined by ICPC-2 codes of T89 or T90
3. Patients exclusively managed by Specialist Out-Patient Clinic (SOPC) on or before baseline\*

To reduce selection bias, the RAMP-HT and usual care subjects will be matched in baseline covariates using the propensity score matching method:

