### (iii) Outcome Measures

The primary outcomes of this study are:

1. The 5-year incidence of CVD among RAMP-HT and usual care HT patients
2. The direct medical costs of RAMP-HT and usual care HT patients with and without complications
3. The ICER of cost per QALY gained by RAMP-HT compared to usual care group

The secondary outcomes of this study are:

4. The 5-year incidence of end stage renal disease (ESRD) and all-cause mortality among RAMP-HT and usual care HT patients
5. The hazard ratio of CVD, ESRD and all-cause mortalities between

RAMP-HT and usual care group

6. The Number-Need-to-Treat (NNT) to reduce one CVD, ESRD and mortality in 5 years by RAMP-HT

(iv) Data Collection

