**HA CMS Data Extraction of Incidence of HT Complications and All-cause Mortality**

Our RAMP-HT QOC study will have collected anonymous 3-year follow up HA CMS data of the cohorts available by November 2015. This study plans to extend the follow up period for an additional 2 years to measure the 5-year incidence of CVD, ESRD and mortality outcomes of these HT patient cohorts from 1 Oct 2011 to 31 March 2017. The data extraction will be carried out by the HA statistics team. Each patient in the cohorts (RAMP-HT and usual care groups) will be observed from baseline to the first occurrence of any of the outcome events until 31 March 2017, with CMS documented diagnoses defined by the relevant ICPC-2 and ICD-9-CM codes below:

1. Cardiovascular disease (CVD) is defined as the presence of any of coronary heart disease (CHD), heart failure or stroke. CHD includes all ischaemic heart disease, myocardial infarction (MI), coronary death or sudden death as indicated by the ICPC-2 K74 to K76 or ICD-9-CM 410.x, 411.x to 414.x, 798.x codes. Heart failure is defined as the ICPC-2 K77 or ICD-9-CM 428.x codes. Stroke (fatal and non-fatal stroke) is defined by the ICPC-2 K89 to K91 or ICD-9-CM 430.x to 438.x codes.
2. End Stage Renal Disease (ESRD) is defined by any of ICD-9-CM 250.3x, 585.x, 586.x, or an estimated Glomerular Filtration Rate (eGFR)  $<15\text{mL/min}/1.73\text{m}^2$ , according to the definition of the National Kidney Foundation.
3. Mortality is defined by a documented death in the Hong Kong Death Registry.

The definitions of each HT complication are determined by the clinician co-investigators and endorsed by clinicians of the HA.

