The Markov models will be analysed by the TreeAge Pro Suite (TreeAge Software, Inc, Williamstown, MA) which can run Markov models.

Data sources are summarized in the table below:

Propose	Item/ unit	Data collection methods
Effectiveness	Incidence of CVD, ESRD and all-cause mortality	Anonymous 5-year dataset of diagnosis record (ICPC-2 and ICD-9-CM) to be extracted by HA statistics team from the HA CMS database #
Direct Medical Costs	(i)Cost of RAMP-HT	(i) In-depth costing of RAMP-HT by 

- set-up and operation costs questionnaires to be completed by HA clusters, GOPCs

- central administration cost questionnaire completed by

	
(ii)Public medical costs of RAMP-HT and usual care group; with complications and without complications
 
(iii)Private direct medical costs
	
Finance Office in HA Head Office
 
(ii)Public healthcare service cost will be estimated by the products of :
 
 
- Public healthcare service utilization rates will be extracted from the 5-year HA CMS dataset.
 
- Unit cost of each healthcare service published in the HKSAR Government Gazette
 
 
(iii)Private medical cost questionnaire administered by telephone survey on 230 RAMP-HT and 218 usual care HT subjects

Calculation of quality adjusted life years (QALY)	SF-6D Health preference values of HT patients without and with complications	SF-12v2 HRQOL data from 410 RAMP-HT and 388 usual care HT patients collected in our previous PRO surveys from May 2013 to March 2014 will be converted to SF-6D preference values.
Cohort Life-time Mortality estimates	
(i) HT related mortality
 
(ii) Mortality from other causes
	
(i)Annual HT-related mortality rates will be estimated from the annual incidence of HT complications and published mortality rates of the respective complications.
 
(ii) Hong Kong standard life table will be used as a

		benchmark for the estimation of mortality from other causes adjusted for age and sex)
--	--	---------------------------------------------------------------------------------------

The Markov modelling will run on the following assumptions:

1. Each HT patient will develop only one HT complication in his/her lifetime.
2. HT patients without complications will not die from HT related death, but may die from other cause of death.

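### The ESRD outcome accepts any 585.x or 586.x code, so it can count earlier-stage kidney disease as ESRD and carry ESRD mortality into the Markov model

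*Combined protocol and SAP*

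**What the plan says.** The second outcome definition, under the heading on CMS extraction of complications and mortality, is "End Stage Renal Disease (ESRD) is defined by any of ICD-9-CM 250.3x, 585.x, 586.x, or an estimated Glomerular Filtration Rate (eGFR", followed by a limit of below 15 mL/min/1.73m². The definition is described as "according to the definition of the National Kidney Foundation". The section adds: "The definitions of each HT complication are determined by the clinician co-investigators and endorsed by clinicians of the HA".

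The second exclusion criterion removes "Patients diagnosed to have Diabetes Mellitus (DM) on or before 31 March 2017, defined by ICPC-2 codes of T89 or T90". The first removes anyone with a complication code on or before baseline, so only newly recorded codes can become events.

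Under Outcome Measures, the secondary outcomes include "The 5-year incidence of end stage renal disease (ESRD) and all-cause mortality among RAMP-HT and usual care HT patients", the ESRD hazard ratio and the ESRD number needed to treat (NNT). ESRD is also one of four complication states in the Markov model that yields the ICER, which is a primary outcome. For mortality in those states, the data-source table combines the annual incidence of complications with "published mortality rates of the respective complications".

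**The concern.** The four criteria are alternatives, so the broadest one decides who can be counted. A patient whose only renal record is a code for mid-stage CKD meets the definition, although the same sentence sets the laboratory threshold at an end-stage value. The two limbs describe different conditions under one name.

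Two things are at stake. The ESRD incidence, hazard ratio and NNT may describe a mixture of recorded CKD and true end-stage disease. The Markov model then places that mixture in a state named ESRD and gives it the mortality of ESRD. An outcome that can be triggered by recording earlier-stage disease is also more open to differences in how closely each arm is examined. The Introduction says of RAMP-HT that "hypertensive complication screening and assessment on patient adherence to treatment are carried out on enrolled patients". Matching on baseline covariates does not correct for detection after baseline.

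**Working it through.** **Step 1: the limbs side by side.** The code meanings are those of ICD-9-CM, the classification the plan names. The plan does not reproduce the code list.

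| Limb | Restriction in the text | What it admits |
|---|---|---|
| 585.x | none on stage | every CKD stage, ESRD, and CKD of unspecified stage |
| 586.x | none | unspecified renal failure |
| 250.3x | none | a diabetes code, in a cohort meant to be free of diabetes |
| eGFR | below 15; silent on repetition | end-stage values |

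No dialysis, transplant or other condition narrows the code limbs. For 250.3x, the diabetes exclusion runs to the end of follow-up, so few such events should remain. They need not be zero, because the exclusion uses ICPC-2 codes only.

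**Step 2: where the outcome goes.** It feeds the secondary outcomes. It also feeds the model's transition from no complication to end-stage renal failure, the hazard ratio applied in the first five years (model assumption 4), and the cost, utility and mortality of the ESRD state. Model assumption 1 allows one complication per lifetime. A patient who enters the ESRD state on an early CKD code therefore cannot later have a modelled stroke, heart failure or coronary event.

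**Step 3: size, by assumption.** The documents give no ESRD rate, event count, power or code mix, so there is no stated figure to reproduce. Let f be the share of counted usual-care events that are not end-stage, and h the true ESRD hazard ratio. Treat events as uncommon and suppose RAMP-HT does not affect the non-end-stage events. Then:

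- counted incidence ÷ true incidence = 1/(1−f)
- observed hazard ratio ≈ f + (1−f)h

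With h = 0.70 (assumed):

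| f (assumed) | Incidence multiplied by | Observed hazard ratio |
|---|---|---|
| 0% | 1.0 | 0.70 |
| 25% | 1.33 | 0.775 |
| 50% | 2 | 0.85 |
| 75% | 4 | 0.925 |
| 90% | 10 | 0.97 |

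For f = 50%: 1/(1−0.5) = 2 and 0.5 + 0.5 × 0.70 = 0.85.

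The NNT behaves differently because it rests on an absolute difference. In units of true usual-care incidence, that difference is 2 × (1−0.85) = 0.30 at f = 50%, the same as 1−0.70 = 0.30 at f = 0. Equal extra events in both arms leave the NNT estimate in place and only make it less precise. It shifts if the extra events differ between arms.

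**Step 4: differential recording.** Suppose there is no true effect on ESRD, and non-end-stage events are r times as frequent in RAMP-HT. The observed ratio is (1−f) + f·r. At f = 50%, r = 1.2 gives 0.5 + 0.6 = 1.10, and r = 0.8 gives 0.5 + 0.4 = 0.90. Nothing in the documents fixes r on either side of 1.

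**Step 5: the model.** A share f of usual-care entrants to the ESRD state receives published ESRD mortality that does not belong to them. The effect on the comparison depends on what RAMP-HT does to those events. If it leaves them alone, entries averted in the first five years are unchanged (0.30 in step 3), but entries are inflated in both arms. If it prevents them in the same proportion, the hazard ratio stays at 0.70 and entries averted at f = 50% become 2 × 0.30 = 0.60, each credited with avoiding ESRD mortality. The size and sign of the change in the ICER cannot be derived from the documents.

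**The case against.** The best defence is that the definitions were set and endorsed by clinicians and tied to a cited kidney-disease source, that ESRD is a secondary outcome and one of four model states, and that the timeline provides for confirming operational definitions with the HA statistics team. Endorsement does not remove the conflict between an unstaged code limb and an end-stage laboratory limb. The confirmation step is an opportunity to repair the definition, but nothing says it will.

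Part of the defence stands. Public costs by complication status come from the same coded cohort. If broad coding brings in milder cases, their lower costs partly match the broad incidence. Utilities come from survey patients grouped by complication status and may partly match too. Mortality is the input that clearly does not.

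A reader might infer several stronger things that the documents do not support:

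- **That the outcome measures mostly non-end-stage disease.** If such codes were 5 to 10 times as frequent as true ESRD, their share would be 5/6 = 83% to 10/11 = 91%. That ratio is an assumption; no code mix is given.
- **That the bias runs against RAMP-HT.** With those ratios and recording 1.2 to 1.5 times as likely in RAMP-HT, a null effect would appear as (1 + 5 × 1.2)/6 = 1.17 to (1 + 10 × 1.5)/11 = 1.45. The recording ratio is assumed. Excluding patients coded by enrolment could remove detected CKD from the RAMP-HT cohort and push the other way, and the programme may also prevent earlier CKD.
- **That 250.3x distorts the result.** It does not fit the cohort, but the diabetes exclusion leaves it little room.
- **That one transient low eGFR is explicitly enough.** The text is silent on confirmation, and this limb is the one clearly tied to end-stage disease.
- **That early CKD codes cut short observation for CVD.** Each patient "will be observed from baseline to the first occurrence of any of the outcome events until 31 March 2017", which can be read that way. The analysis section models each first complication event, which may mean separate follow-up for each outcome.

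**Conclusion.** The definition is wrong as written and should be fixed. Followed literally, it can count non-end-stage kidney disease as ESRD, because 585.x and 586.x carry no stage limit while the laboratory limb requires eGFR below 15. This rests on the wording of the definition and on the ICD-9-CM meaning of the codes.

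The share of such events is unknown, and so is the direction of any bias between arms; both should be reported as unknown. The figures in the working are illustrations over assumed shares, not estimates for this cohort. The firmest consequence is the mismatch between published ESRD mortality and a more broadly coded incidence, which affects the ICER by an amount the documents do not allow one to calculate. The ESRD hazard ratio may also be diluted, and both it and the NNT may be sensitive to screening intensity.

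**What to change.** For the outcome, limit the code limb to end-stage subcodes: 585.6, plus 585.5 if stage 5 is meant to correspond to eGFR below 15. Keep the eGFR limb and remove 250.3x. Keep the wide code list for baseline exclusion, so that the 8,681 matched pairs are unchanged. Report the other 585 and 586 codes as a separate CKD outcome, outside the ESRD health state.

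If the CMS does not record 585 subcodes reliably, report the code mix by arm. Then run a strict analysis (eGFR below 15 or an end-stage code) beside the broad one for the hazard ratio, the NNT, the Markov transition and the ICER.

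Use a repeat-eGFR requirement only as a sensitivity analysis, because meeting it depends on surviving and being retested, and retesting may differ between arms.

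The change uses codes and eGFR values the definition already calls for, and can be made when the operational definitions are confirmed with the HA statistics team. It costs ESRD events, widens the intervals, and may lose true ESRD recorded only under 586.

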### **Direct Medical Costing Studies**

The costing studies will be evaluated from the healthcare provider's perspective.

#### *(i) In-depth costing of RAMP-HT*

The cost of RAMP-HT comprises of three components: (a) set-up costs; (b) ongoing intervention costs; and (c) central administrative costs. Set-up costs refer to one-off expenses incurred in the course of setting up the programme, which include costs related to staff training, additional equipment, information technology and infrastructure. Ongoing intervention costs refer to the recurrent costs for the programme operation and maintenance, which include costs of staff, printing and consumables in the clinics. The evaluation of the set-up costs will be primarily based on the data reported by the clusters, who are responsible for maintaining detailed inventory of supplies purchased and distributed to the clinics. Central administrative costs refer to recurrent costs incurred by the GOPCs for running RAMP-HT (i.e. project team cost in Head Office).

The set-up and intervention costs will be collected by two sets of questionnaires to be completed by RAMP-HT programme co-ordinators of the HA clusters and GOPCs that provide the RAMP-HT service (Appendix D); The central administration costs will be collected from the Finance Office in HA Head Office by a structured questionnaire. These questionnaires are adapted from the costing questionnaires that were used in our in-depth study on the cost-effectiveness analysis of RAMP-DM that had proven feasibility and validity (HHSRF # EPC\_HKU-1A).

#### *(ii) Direct Medical Costs of HT patients*

The medical cost analysis will focus on the direct medical costs involved in the care of HT patients without or with specific HT complications (i.e. CHD, heart failure, stroke and ESRD) in both public and private healthcare sectors; indirect cost (e.g. opportunity cost) and non-medical costs (e.g. transportation cost, carer cost) will not be measured.

Public medical costs will be estimated from products of the unit costs (published in the HKSAR Government Gazette and Hospital Authority ordinance (Chapter 113) of charges for non-entitled persons) and the utilization rates of 1) dispensed drugs (*note: self-financed drugs will be considered as private medical cost, see below*), 2) laboratory tests and investigations, 3) healthcare services including general outpatient clinics (GOPC), specialist outpatient clinics (SOPC), allied health services (e.g. dietician, physiotherapist or occupational therapist), accident and emergency (A&E) department and 4) admissions to hospital in the 12 months before baseline and at 12, 24, 36, 48 and 60 months after study enrolment for each patient in the study cohorts. The data extraction will be carried out by the HA statistics team.

Private direct medical costs include the cost of all private Western doctor and Chinese medicine practitioner consultations, private hospitalisation and self-medications inclusive of self-financed medications prescribed by the HA. 598 HT patients (307 RAMP-HT patients and 291 usual care patients) who were recruited from HA GOPCs for the longitudinal evaluation of patient reported outcomes (PRO) in the evaluation of QOC RAMP-HT study from May 2013 to March 2014 will be invited to complete a “private medical cost of HT questionnaire” (Appendix E) by telephone. The questionnaire is adapted from the costing questionnaire that was used in our in-depth study on the cost-effectiveness analysis of RAMP-DM that had proven feasibility and validity (HHSRF # EPC\_HKU-1A).

### **Health Preference of HT Patients**

Health-related quality of life (HRQOL) measured by the SF-12v2 collected in our previous PRO surveys of the evaluation of QOC of RAMP-HT study from May 2013 to March 2014 will be converted to SF-6D health preference values by the HK algorithm for HT patients with or without complications (CVD, end stage renal disease).

#Our team has successful collaboration with the HA statistics Department to extract the relevant data as part of our evaluation of QOC and short-term effectiveness of RAMP-HT study (HHSRF commissioned project EPC\_HKU-2). The detailed data schema is attached in the Appendix F.

(v) Data processing and analysis

**Long Term Effectiveness of RAMP-HT**

Descriptive statistics will be performed on the clinical parameters (e.g. blood pressure (BP), lipid profile, BMI) and incidence of CHD, heart failure, stroke, ESRD, HT-related mortality and all-cause mortalities of the RAMP-HT and usual care cohorts. Differences in each outcome between groups will be tested using independent t-tests for continuous variables such as mean BP, or chi-square tests for categorical variables such as proportion of patients with BP control or CVD incidence. The number needed to treat to reduce one CVD, each specific HT complication and death by RAMP-HT will be calculated from the unadjusted 5-year rates between RAMP-HT and usual care HT cohorts.

Multivariable Cox proportional hazards regression will be performed to estimate the adjusted effect of RAMP-HT on the dependent variable of each first HT complication event, adjusting for all baseline covariates of patients. Cox model has been widely used to evaluate the effectiveness of primary care intervention in previous study. For each model, survival curves will be estimated by Kaplan-Meier method and the differences between RAMP-HT and usual care groups will be compared using the

log-rank test. The effectiveness of RAMP-HT will be measured by Hazard ratio with 95% confidence intervals in the regression models. Predictive accuracy of Cox models will be assessed and compared using Harrell's discrimination C-index, ranging from zero to one. A value of 0.5 indicates no predictive discrimination, and values of 0 or 1.0 indicate perfect separation of patients. Goodness-of-fit for Cox regression model will be assessed using Akaike information criterion and Bayesian information criterion.

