##### **(ii) Subjects**

All patients who have enrolled into the RAMP-HT between 1 Oct 2011 and 31 March 2012, fulfilled the following inclusion criteria and without any exclusion criterion will be included in the RAMP-HT cohort. The same number of matched patients receiving usual care in GOPCs who have never enrolled into RAMP-HT on or before 31 March 2017, fulfilled the following inclusion criteria and without any exclusion criterion will be randomly selected from the HA clinical management system (CMS) to form the usual

care cohort.

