#### *Propensity Score Matching*

Propensity score matching was first introduced in 1983. The technique summarises relevant baseline characteristics of each eligible HT patient into a single-index variable (the propensity score); HT patients in usual care will be matched to patients in the RAMP-HT group based on the value of the propensity score. The propensity score will be generated for each patient by logistic regression, modelling the RAMP-HT as dependent variable and baseline covariates of patients as independent variables. The propensity score mapping will be performed by using the “psmatch2” command with one-to-one matching without replacement and a callipers of 0.001 approach in the STATA.

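### The matched-cohort comparisons make no allowance for clustering by clinic (or, less importantly, for the 1:1 pairs), so precision for the primary CVD result may be overstated

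*Combined protocol and SAP*

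**What the plan says.** Section d(ii), Propensity Score Matching, forms the cohorts by "one-to-one matching without replacement and a callipers of 0.001 approach". The covariates listed under Baseline Covariates are all patient characteristics; neither clinic nor Hospital Authority cluster is among them.

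Section d(v), Long Term Effectiveness of RAMP-HT, then sets out the arm comparisons. Continuous outcomes: "Differences in each outcome between groups will be tested using independent t-tests for continuous variables such as mean BP". Binary outcomes, including the primary one: "chi-square tests for categorical variables such as proportion of patients with BP control or CVD incidence". Time to event: log-rank tests and a Cox model "adjusting for all baseline covariates of patients". The effect measure is given as follows: "The effectiveness of RAMP-HT will be measured by Hazard ratio with 95% confidence intervals in the regression models". The variance estimator behind those intervals is not stated. Cost Analysis of RAMP-HT adds a one-sided independent t-test for direct medical costs.

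No section mentions a paired test, a robust or clustered variance, a frailty term or a clinic effect, and the sample size calculation includes no design effect.

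Two passages bear on clinics. The in-depth costing section sends questionnaires to "GOPCs that provide the RAMP-HT service", which implies that not every GOPC does so. Section d(ii), Subjects, defines the comparison group by patient: "The same number of matched patients receiving usual care in GOPCs who have never enrolled into RAMP-HT on or before 31 March 2017".

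**The concern.** RAMP-HT is organised and delivered through clinics by a multidisciplinary team. If some clinics enrolled many of their patients and others few or none, exposure is partly a property of the clinic. Outcomes may also be alike within a clinic, through its catchment, its prescribing or the way it records the diagnosis codes from which CVD is ascertained. When exposure and outcome both cluster, standard errors that assume independent patients are too small. Adjusting for patient covariates does not cure this.

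The matched pairs are a second structure left out of the stated tests. Positive correlation within pairs makes an unpaired interval slightly too wide, so this error runs in the opposite direction.

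At stake is the claimed precision of the primary comparison. The planned difference in 5-year CVD incidence is small (7% against 8%), so a material understatement of the standard error could change the conclusion.

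**Working it through.** **Any allowance in the plan's own figures.** The plan gives no design effect, ICC or clinic count to reproduce. Its only related figure is 7,116 per group (7% against 8%, 90% power, 5% level). The usual two-proportion formula, two-sided and with no clustering, gives

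n = [1.960 × √(2 × 0.075 × 0.925) + 1.282 × √(0.07 × 0.93 + 0.08 × 0.92)]² / 0.01² = 14,577 per group.

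The stated figure lies below even this, so it contains no hidden margin for clustering. Why the two differ is a separate matter, and nothing below depends on it.

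**Inputs.**
- From the documents: 8,681 per group, so 2 × 8,681 = 17,362 patients.
- Assumed, because the documents are silent: number of clinics K = 40 to 100; ICC = 0.001 to 0.01; pair correlation ρ = 0.02 to 0.10.
- Worst case: each clinic lies wholly in one arm.

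**Clinics, worst case.** With m = 17,362/K, the design effect is DE = 1 + (m − 1) × ICC. The true standard error is √DE times the naive one. The true size of a nominal two-sided 5% test is 2 × [1 − Φ(1.96/√DE)].

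| | Mild end | Severe end |
|---|---|---|
| K; ICC | 100; 0.001 | 40; 0.01 |
| m | 173.6 | 434.1 |
| DE | 1 + 172.6 × 0.001 = 1.17 | 1 + 433.1 × 0.01 = 5.33 |
| √DE | 1.08 | 2.31 |
| True SE larger than naive SE by | 8% | 131% |
| Naive SE too small by (1 − 1/√DE) | 8% | 57% |
| True size of a 5% test | 7.0% | 39.6% |

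**Clinics, partial concentration.** Let c be the within-clinic correlation of exposure: 1 if exposure is set wholly by clinic, 0 if the arm mix is the same everywhere. Then DE = 1 + (m − 1) × ICC × c.
- c = 0.5: DE 1.09 to 3.17, true size 6.0% to 27.1%.
- c = 0.2: DE 1.03 to 1.87, true size 5.4% to 15.1%.
- c near 0: the inflation largely disappears.

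**Pairs.** For pair correlation ρ, a paired interval is √(1 − ρ) times the width of the unpaired one.
- ρ = 0.02: √0.98 = 0.990, so the unpaired interval is about 1% too wide; true size 4.8%.
- ρ = 0.10: √0.90 = 0.949, so about 5% too wide; true size 3.9%.

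**Which comparisons the pairing point reaches.** It reaches the matched cohorts only. The private-cost survey (307 against 291 recruited, 230 against 218 expected to respond) and the SF-6D data (410 against 388) have unequal arms and are not described as pairs. An unpaired test is consistent with that design.

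**The case against.** The strongest reply is that separation of the arms by clinic is an inference. It rests on one phrase in the costing section, whose purpose there is to say who completes a questionnaire. That phrase does not say which clinics lacked the programme between October 2011 and March 2012. Usual care is defined by the patient never having enrolled, so its members may attend the same clinics as enrollees, and then much of the inflation cancels. Shared coding practice within clinics is plausible but not documented. This stands: the size cannot be established from the documents, and the severe end needs the fewest clinics, the highest ICC and complete separation together.

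It is also fair to say that the pairing issue is small and conservative, and that the Cox model already conditions on the matching covariates. That stands too, and pairing is therefore secondary. Patient-level adjustment does not deal with clinic effects, however.

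Finally, the plan is silent on the Cox variance, so a robust estimator is not ruled out. But the named t-tests and chi-square tests do assume independent patients, and they cover the primary CVD incidence.

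A reader might infer that every between-arm interval and p-value is wrong, or that the 5% level is certainly missed. The documents do not support this. They do not show the arms to be in different clinics, the two omissions act in opposite directions, and pairing is not at issue for the private-cost and SF-6D samples.

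**Conclusion.** The point holds in a conditional form. The stated analyses of the matched cohorts do not protect against clinic clustering, and intervals for the primary CVD comparison may be too narrow to the extent that exposure is concentrated by clinic. Under the assumed ranges, the worst case runs from trivial to serious (true size 7% to 40%), and partial concentration still gives 5.4% to 27.1%. These are illustrations under assumed clinic counts and ICCs, not estimates for this study. The documents do not let a reader tell where in the range it falls, which is itself the reason to fix the variance estimator in advance. Ignoring the pairs widens intervals by about 1% to 5% under the assumed correlations, and does not offset the severe end. The change should be made because it is cheap and bears on the primary result.

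**What to change.** 1. Obtain the clinic identifier for every patient in the matched cohorts, if the data schema (Appendix F, not among the pages available here) does not already hold it. The Timeline includes confirming the schema with the Hospital Authority statistics team and a later 5-year extraction, so there is an opportunity to ask for it.
2. Specify clinic-clustered robust standard errors for the Cox hazard ratios. Do the same for the unadjusted arm comparisons of CVD, the other outcomes and public costs, for example by regression on arm with clustered errors in place of the independent t-test and chi-square test.
3. Report the number of clinics and the arm mix by clinic, so that readers can judge how far exposure follows clinic.
4. As a secondary step, use pair-robust variance in the matched cohorts. Pairs may straddle clinics, in which case one clustering variable does not cover both structures; use two-way clustering or a sensitivity analysis there.

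The cost is possibly one extra extracted field and some added analysis specification. Intervals may widen.
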